## **Vulnerable Patient Populations**

### Pregnancy

Although no potential risks have been identified in nonclinical studies, the effect of BCL-2 inhibition on pregnancy has not been fully characterized. Venetoclax resulted in increased post-implantation loss, and decreased fetal body weights were observed in the mouse embryofetal development study at the highest dosage administered. Venetoclax was not teratogenic, and there were no other effects on development or fertility. Two pregnancies have been reported in the program, including one pregnancy of a partner. Venetoclax should not be administered to pregnant women. Female subjects enrolled in clinical studies with single agent venetoclax must be surgically sterile, postmenopausal (for at least 1 year), or have negative results for a pregnancy test. Female subjects enrolled in clinical studies with venetoclax must agree to use contraception from initial study drug administration until 30 days after the last dose of study drug. Venetoclax must be discontinued if a female subject becomes pregnant (i.e. subject will be excluded from the study).

Male subjects enrolled in clinical studies with single agent venetoclax must agree to use contraception from initial study drug administration until 30 days after the last dose of study drug.

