### 4.1 Inclusion criteria

#### **Inclusion criteria for both escalation and expansion phase:**

- Ability to understand and the willingness to sign a written informed consent. A signed informed consent must be obtained before screening.
- AML according to WHO-2016 criteria, excluding acute promyelocytic leukemia
- Relapsed from first or second CR after 1-2 cycles of standard induction chemotherapy (which must have included cytarabine with an anthracycline or anthracenedione), including relapse after allogeneic stem cell transplantation (dose escalation and expansion part)
- Age 18-75 years
- Fit for intensive chemotherapy, defined by
  - ECOG 0-2, life expectancy > 3months
  - Adequate hepatic function: ALAT/ASAT/Bilirubin  $\leq 2.5 \times \text{ULN}^*$ 
    - \* unless considered due to leukemic organ involvement

Note: Subjects with Gilbert's Syndrome may have a bilirubin > 2.5  $\times$  ULN per discussion between the investigator and Coordinating investigator.

- Adequate renal function assessed by serum creatinine  $\leq 1.5 \times \text{ULN}$  OR creatinine clearance (by Cockcroft Gault formula)  $\geq 50 \text{ mL/min}$

- Patient is afebrile and hemodynamically stable for at least 72 hours at the time of study medication initiation.
- Male subjects must agree to refrain from unprotected sex and sperm donation from time point of signing the informed consent until 30 days after the last dose of study drug.
- Women must fulfill at least one of the following criteria in order to be eligible for trial inclusion:
  - Post-menopausal (12 months of natural amenorrhea or 6 months of amenorrhea with Serum FSH > 40 U/ml)
  - Postoperative (i.e. 6 weeks) after bilateral ovariectomy with or without hysterectomy
  - Women of childbearing potential must have a negative serum pregnancy test performed within 7 days before the first dose of study drug.
  - Continuous and correct application of a contraception method with a Pearl Index of <1% (e.g. implants, depots, oral contraceptives, intrauterine device – IUD) from time point of signing the informed consent until 30 days after the last dose of study drug.

Note: At present, it is not known whether the effectiveness of hormonal contraceptives is reduced by venetoclax. For this reason, women should use a barrier method in addition to hormonal contraceptive methods.
  - Sexual abstinence
  - Vasectomy of the sexual partner

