### **4.3 Justification for gender selection**

Men and women (postmenopausal or using appropriate contraception) will be enrolled in this study. The proportion of men and women enrolled in this study depends only on the availability of subjects at the study site. Due to the severity of the underlying disease, the treatment of men as well as women is justified. There is no data suggesting increased or decreased activity of the study drug in either gender.

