- c All subjects must receive tumor lysis prophylaxis prior to and during treatment, including chemistries at 24, 48 and 72 hours after administration of the designated cohort dose. For details on tumor lysis prophylaxis and management, refer to section [5.4.5](#) Management of Tumor Lysis Syndrome (TLS) and [Appendix 2](#) – Recommendations for Initial Management of Electrolyte Imbalances and Prevention of Tumor Lysis Syndrome (TLS) for further information. Subjects in the expansion stage only require TLS prophylaxis and management 24, 48, and 72 hours after administration of the designated cohort dose, if clinically necessary.
- d TLS chemistry tests (calcium, inorganic phosphorus, potassium, uric acid, creatinine) on each day of new dose of venetoclax at pre-dose, 6-8 hours and 24 ( $\pm$  2) hours post-dose (see section [5.4.5](#))
- e local bone marrow assessment: cytomorphology including cytochemistry, immunophenotyping, cytogenetics, molecular diagnostics
- f day 18: only BM-assessment for cytomorphology incl. cytochemistry
- g samples for central diagnostics (Hema Lab Dresden): 5 bone marrow and 2 peripheral blood smear slides for cytomorphology and 10ml heparinized bone marrow for immunophenotyping
- h Women of childbearing potential must have a negative serum pregnancy test performed **within 7 days** before first dose of venetoclax
- i Remission Assessment-visit on day 28-45 is required for all patients regardless a subject has prematurely terminated the study treatment for any reason or not (except for death or withdrawn ICF).
- k All patients will be followed-up after last study visit for survival, remission status, further AML therapies (regimes and start dates) and second primary malignancies for minimum 24 months, either by phone calls or visits.
- l vital signs: blood pressure, heart frequency and temperature
- m height only at Screening
- n Virus diagnostics (according to clinical standards): HBs-antigen, HBs-antibody (if positive HBs-antibody – HBV DNA required), anti-HBc, anti-HCV IgG (if positive anti-HCV IgG – HCV RNA required)
- o ancillary research: collection of 9 ml peripheral blood (pB) in EDTA-tube and 5 ml bone marrow (BM) in EDTA-tube + 3 ml heparinized BM at screening, remission assessment and in case of progress (see section [6.5](#))

Table 10: Visit schedule maintenance therapy

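### Section 4.1 lists the negative pregnancy test as an alternative to contraception, so as printed it admits a woman whom section 4.3 does not

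*Protocol*

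**What the plan says.** Protocol section 4.1, in the criteria common to both phases, introduces the rule for women with "Women must fulfill at least one of the following criteria in order to be eligible for trial inclusion". Six items follow:

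1. post-menopausal status
2. status after bilateral ovariectomy
3. the pregnancy test: "Women of childbearing potential must have a negative serum pregnancy test performed within 7 days before the first dose of study drug"
4. a contraception method with a Pearl Index below 1%, from consent until 30 days after the last dose
5. "Sexual abstinence"
6. "Vasectomy of the sexual partner"

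Four other places bear on the same women:

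- **Section 4.3** describes the population of this trial: "Men and women (postmenopausal or using appropriate contraception) will be enrolled in this study".
- **Section 1.3.2 (Pregnancy)** gives general guidance for venetoclax studies: "Female subjects enrolled in clinical studies with venetoclax must agree to use contraception from initial study drug administration until 30 days after the last dose".
- **Table 9, footnote h** (section 6.1) states the test on its own: "Women of childbearing potential must have a negative serum pregnancy test performed", again within 7 days before the first venetoclax dose.
- **Section 4.2** excludes pregnant or breastfeeding women and says nothing about women who use no contraception.

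**The concern.** Five of the six items are reasons why a woman is not expected to conceive during treatment. The sixth, the test, shows only that she is not pregnant shortly before the first dose. Because any one item is enough, the test can stand in for the other five.

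Section 6.6 makes the day 1 check of the inclusion and exclusion criteria the step that permits enrolment, and section 11.1 asks for strict adherence to the protocol. A site that applies the printed list could therefore enrol a woman outside the population in section 4.3 and still be following section 4.1. What is at stake is possible fetal exposure to study treatment. Section 1.3.1 reports embryofetal toxicity in mice (more post-implantation loss and lower fetal weights at the highest dosage, though no teratogenicity), and section 1.3.2 says that venetoclax should not be given to pregnant women.

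**Working it through.** The plan gives no figure on this point, so the check is logical. The section 4.1 rule is a disjunction of six items. I applied it to the four possible situations of a woman of childbearing potential, who by definition meets neither the post-menopausal nor the post-ovariectomy item. A method here means contraception, abstinence or partner vasectomy as listed in section 4.1. For sections 4.3 and 1.3.2 the table takes the method to be contraception.

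| Situation | 4.1 list as printed | Excluded by 4.2? | Table 9 footnote h | 4.3 | 1.3.2 |
|---|---|---|---|---|---|
| A. Negative test, no method | met (test item) | no | met | **not met** | **not met** |
| B. Negative test, with a method | met | no | met | met | met |
| C. No test, with a method | met (method item) | no | **not met** | met | met |
| D. No test, no method | not met | no | not met | not met | not met |

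Situation by situation:

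- **A** passes the inclusion list, the exclusion list and the visit schedule, yet falls outside section 4.3. Nothing in 4.1, 4.2 or the synopsis criteria separately requires contraception of her.
- **B** is consistent throughout.
- **C** satisfies the opening words of the list, but footnote h still requires the test, so this gap is closed elsewhere.
- **D** is stopped by section 4.1 itself.

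Only A remains open.

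The conflict with section 4.3 is the more direct one, because 4.3 describes who is enrolled in this study. Section 1.3.2 is guidance on venetoclax studies in general and is weaker support. Its list that allows a negative test as an alternative to sterility or menopause does not rescue section 4.1: that list is limited to single-agent venetoclax, and the contraception sentence that follows has no such limit.

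The rule for men in section 4.1 has no comparable opening. It is an unconditional agreement to refrain from unprotected sex and sperm donation.

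**The case against.** The strongest reply is that the test item was meant as a stand-alone rule that ended up inside the list. It is a full sentence with its own must, while its neighbours are mostly short status phrases, and footnote h repeats it independently. Indentation in the available text is also not fully reliable: the renal-function item sits apart from the hepatic one, although the synopsis groups both under fitness. On this reading a woman of childbearing potential needs the test and must also qualify through another item, broadly as section 4.3 expects.

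That is probably the intent. But it shows that the wording needs correcting. As printed, the item counts towards the required one, and the day 1 check is made against the printed criteria.

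Two further replies stand in part:

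- Section 1.3.2 cannot serve as a strict yardstick. Taken literally it asks contraception of all female subjects, including postmenopausal and sterile women.
- Section 4.3 lies within the study-population chapter, so the intended restriction is in the document. It is not in the inclusion or exclusion lists, however.

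Other safeguards exist and should be credited. Pregnancy is an exclusion, Table 10 has a test before maintenance, and sections 1.3.2 and 4.4.1 call for venetoclax to stop on pregnancy. None of them requires contraception at entry.

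**Conclusion.** The inconsistency is real and narrow. Section 4.1 as printed admits a woman of childbearing potential on a negative test alone. This conflicts with section 4.3 and is out of line with the guidance in section 1.3.2. The conclusion rests on reading the test as one of the alternatives in the list, as the text presents it.

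The point is one of participant safety and eligibility wording. It has no bearing on the sample size, the primary analysis or the determination of the maximum tolerated dose.

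A reader might infer more than the protocol supports:

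- **That every enrolled woman of childbearing potential is affected.** The faulty rule applies to all of them, but its consequence reaches only those who use none of the listed methods. The protocol gives no number for them.
- **That unprotected exposure would run for 12 × 28 = 336 days of maintenance.** Under sections 3.4 and 5.4.3 maintenance is open only to patients in CR or CRp with neutrophil recovery and no other post-remission option. The 336 days arise only if all twelve cycles are given.
- **That the absence of scheduled pregnancy tests during maintenance is part of the error.** It contradicts no other part of the protocol and is not part of this point.

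**What to change.** Reconcile section 4.1 with section 4.3, section 1.3.2 and footnote h of Table 9. Take the pregnancy test out of the list of alternatives and state it as a separate, additional requirement for women of childbearing potential, with the 7-day window already given. Leave the other five items unchanged. The sponsor should confirm at the same time that the short description in section 4.3 is meant to cover all five, since it does not name ovariectomy, abstinence or partner vasectomy.

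The change moves one item and adds no test, visit or method. Its cost is that a woman of childbearing potential who uses none of the listed methods would no longer be eligible, which is in line with section 4.3.

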**Inclusion criteria applying for expansion phase (Phase II) only:**

- Primary refractory after 1-2 cycles of standard induction chemotherapy (100 to 200 mg/m^2 cytarabine over 7-10 days plus anthracycline or mitoxantrone over 3 days) or relapsed from first or second CR after 1-2 cycles of standard induction chemotherapy (which must have included cytarabine with an anthracycline or anthracenedione), including relapse after allogeneic stem cell transplantation

**4.2 Exclusion criteria**

- Acute promyelocytic leukemia (AML M3)
- CNS involvement or subjects with extramedullary disease only
- Known hypersensitivity to excipients of the preparation or any agent given in association with this study including cytarabine or mitoxantrone
- Intended hematopoietic stem cell transplantation planned as early conditioning from aplasia without previous blood count recovery

- Cumulative previous exposure to anthracyclines of >410 mg/m^2 doxorubicin equivalents
- Acute GVHD ≥ grade 2, extensive chronic GVHD or requiring systemic immunosuppressive therapy within 2 weeks prior to start of study treatment
- HIV infection (due to potential drug-drug interactions between antiretroviral medications and venetoclax, as well as anticipated venetoclax mechanism-based lymphopenia that may potentially increase the risk of opportunistic infections).
- Inability to swallow oral medications
- Any malabsorption condition
- Treatment with strong and moderate CYP3A inhibitors (see [Appendix 1](#)) during screening
- Cardiovascular disability status of New York Heart Association (NYHA) Class ≥ 2.  
Class 2 is defined as cardiac disease in which patients are comfortable at rest but ordinary physical activity results in fatigue, palpitations, dyspnea, or anginal pain.
- Chronic respiratory disease that requires continuous oxygen use.
- White blood cell count > 25 × 10^9/L. Note: Hydroxyurea is permitted to meet this criterion.
- AML relapse treatment with any investigational or commercial drug within 14 days before enrolment. Hydroxyurea is allowed until enrolment to control peripheral WBC counts. Toxic effects of previous investigational drug treatment have to recover to Grade <2.
- Substance abuse, medical, psychological, or social conditions that may interfere with the subject's cooperation with the requirements of the trial or evaluation of the study results
- Pregnant or breastfeeding women.  
Breastfeeding has to be discontinued before onset of and during treatment and should be discontinued for at least 3 months after end of treatment.
- History of active or chronic infectious hepatitis unless serology demonstrates clearance of infection  
(Occult or prior hepatitis B virus (HBV) infection (defined as negative hepatitis B surface antigen and positive total hepatitis B core antibody) may be included if HBV DNA is undetectable, provided that they are willing to undergo monthly DNA testing. Patients who have protective titers of hepatitis B surface antibody after vaccination or prior but cured hepatitis B are eligible. Patients positive for hepatitis C virus antibody are eligible provided PCR is negative for HCV RNA.)
- History of clinically significant liver cirrhosis (e.g., Child-Pugh class B and C).
- Live-virus vaccines given within 28 days prior to the initiation of study treatment

### **4.3 Justification for gender selection**

Men and women (postmenopausal or using appropriate contraception) will be enrolled in this study. The proportion of men and women enrolled in this study depends only on the availability of subjects at the study site. Due to the severity of the underlying disease, the treatment of men as well as women is justified. There is no data suggesting increased or decreased activity of the study drug in either gender.

### **4.4 Withdrawal of subjects from study**

#### **4.4.1 Withdrawal**

Participation in the trial is voluntary. A subject has the right to withdraw from the study at any time for any reason without any consequences for the further medical treatment. If s/he chooses to withdraw, the investigator will be informed immediately. After withdrawal of the study consent, the subject will be treated according to standard of care. Furthermore, the investigator has the right to terminate the participation of any subject at any time, if s/he deems it in the participant's best interest. The reason and circumstances for study discontinuation will be documented in the participant's eCRF.

#### **Reasons for patient's premature end of study might be:**

- At their own request or at the request of their legally acceptable representative
- If, in the investigator's opinion, continuation of study would be harmful to the subject's wellbeing or if the subject is no longer eligible for the study (e.g. development of any intercurrent illness).
- At specific request of the sponsor and in liaison with the investigator (e.g. obvious non-compliance, safety concerns)
- Use of illicit drugs or other substances abuse that may, in the opinion of the investigator, have a reasonable chance of contributing to toxicity or otherwise confound the results
- Subjects who experience a relapse or are diagnosed with resistant disease throughout the trial, unless the investigator (in consultation with the sponsor) deems that continued treatment is appropriate.
- The development of a second malignancy that requires a different treatment
- Interruption of venetoclax >28 days during maintenance therapy

A withdrawn subject is referred to as either "screening failure" or "dropout (= premature end of treatment)" depending on the time point of withdrawal.

A subject who discontinues study treatment prematurely for any reason is defined as a “dropout” if the subject has already been administered at least 1 dose of the study drug. Data of drop-out patients will be analyzed intention-to treat as part of the full analysis set (FAS), see [section 8.2.2.1](#).

A subject who, for any reason (e.g. failure to satisfy the selection criteria), terminates the study prior to the first dose of study drug is regarded as a “screening failure”.

In all cases, the reason for withdrawal must be recorded in the electronic case report form (eCRF) and the subject’s medical record. If a patient has withdrawn his consent, it has also to be documented in the subject’s medical record whether the patient has agreed to further documentation of personal data during follow-up period.

Treatment with the Investigational medicinal product (IMP) venetoclax should be stopped for the following reasons and has to be reported in the appropriate page of the eCRF:

- Severe allergic reactions, such as exfoliate erythroderma, anaphylaxis, or vascular collapse, related to the study drug
- Experience of DLT
- Subjects with a beta human chorionic gonadotropin test consistent with pregnancy. Pregnancy will be reported along the same timelines as SAEs (see [section Reporting of SAEs and SARs](#)).
- Intolerable toxicity or recurrent toxicities requiring dose reduction venetoclax below 50 mg or 10 mg

These patients stay in the trial and have to perform all visits and assessments according to visit schedule until V8 – Remission Assessment.

Details for the premature termination of the whole study are provided in section [10](#).

#### **4.4.2 Replacement**

Subjects who experience a DLT will NOT be replaced.

In the dose escalation part of the trial (i.e. phase I), following patients should be replaced to ensure the required number of evaluable subjects per cohort:

- subjects not experiencing a DLT who have taken less than the required study treatment as described in section [3.2.1](#)
- subjects with incomplete DLT evaluation period due to any reason other than a DLT even if they have received the required study treatment (section [3.2.1](#))

In the expansion part of the trial (i.e. phase II), subjects will not be replaced.

## 5 Study treatment

### 5.1 Investigational medicinal product (IMP) venetoclax

#### 5.1.1 Description of the IMP

The study drug provided is venetoclax. The study drug will be supplied as 10mg, 50 mg and 100 mg film coated tablets in blisters or bottles. See current Investigator's Brochure for further characteristics, mechanism of action, preclinical activity, side effects, pharmacokinetics and results of clinical trials.

#### 5.1.2 Packaging and labeling

The pharmaceutical manufacturer AbbVie is responsible for quality control, labelling, batch release, packaging and shipment to the central distribution pharmacy. Venetoclax will be labeled according to the requirements of local law and legislation. Label text will be approved according to the Sponsor's procedures. A complete record of batch numbers and expiry dates of all study treatment will be maintained in the sponsor study file.

The clinical trial sites will be supplied with a venetoclax supply sufficient for one full cycle of V-MAC for one patient, i.e.

- 1 blister of "**8 x 50mg tablets, child resistant blister cards**" (sufficient for days 1-3) and
- 4/6 blisters of "**8 x 100 mg tablets, child resistant blister cards**" (sufficient for days 4-10/14)

For maintenance treatment, the clinical trial sites will be supplied with 3 bottles, each containing "**120 x 100mg tablets, child resistant bottles**", re-supply every 3 months on request of trial site.

If a dose reduction of venetoclax is necessary because of co-administration of strong and/or moderate CYP3A inhibitors during the expansion phase and maintenance, the patient will be supplied with sufficient blisters of "**16 x 10mg tablets, child resistant blister cards**".

Each blister or bottle carries a label as shown in [Figure1](#), depending on the dose it contains.

TUD-RELAX1-070 (A16-332)	
Technische Universität Dresden, Medizinische Fakultät, [name], [contact]	
Prüfpräparat für durch Prüfarzt initiierte Klinische Prüfung	
EudraCT-Nummer: 2018-003025-28	
Venetoclax 50 mg Filmtablette	
Nur zur oralen Einnahme.	8 Tabletten
Name des Prüfarztes: _____	
Telefonnummer des Prüfarztes: _____	
Nach Anweisung des Prüfarztes einnehmen. Bei 15 - 25°C lagern.	
Bitte geben Sie das gebrauchte oder ungebrauchte Prüfpräparat wie mit Ihrem Prüfpersonal vereinbart wieder zurück.	
Für Kinder unzugänglich aufbewahren. Zur Klinischen Prüfung bestimmt.	
1) Kit-Nr.: XXXXXXXX	
2) Ch.-B.: XX-XXXXXX	Patientennr.: _____
3) Verwendbar bis: XX-XX-XXXX	Abgabedatum: _____

[Figure 1](#): sample of packaging label of venetoclax

